7.0 TREATMENT PLAN

TREATMENT	PAZOPANIB RUN-IN ^A	CYCLES 1 AND 2 ^B	CYCLES 3 AND 4 ^C	PRE- OP RT ^D	SURGERY ^E	CYCLES 5 AND 6 ^B	POST-OP RT ^F
DOXORUBICIN		75 MG/M2 CIVI OVER 3 DAYS, EACH CYCLE WEEKS 3-8	75 MG/M2 CIVI OVER 3 DAYS, EACH CYCLE WEEKS 9-14	WEEKS 16-21	2-4 WEEKS AFTER COMPLE- TION OF PRE- OPERATIVE THERAPY	75 MG/M2 CIVI OVER 3 DAYS, EACH CYCLE 2-4 WEEKS AFTER SURGERY	2-4 WEEKS AFTER COMPLETION OF CHEMO-THERAPY
IFOSFAMIDE		2 GM/M2 IV, DAYS 1-5, EACH CYCLE WEEKS 3-8 (6-DAY WASHOUT AFTER PAZOPAN -IB	2 GM/M2 IV, DAYS 1-5, EACH CYCLE WEEKS 9-14			2 GM/M2 IV, DAYS 1-5, EACH CYCLE 2-4 WEEKS AFTER SURGERY	

TREATMENT	PAZOPANIB RUN-IN A	CYCLES 1 AND 2B	CYCLES 3 AND 4C	PRE- OP RT D	SURGERY E	CYCLES AND 6B 5	POST-OP RTF
MESNA^I		AFTER EACH DOSE OF IFOS	AFTER EACH DOSE OF IFOS			AFTER EACH DOSE OF IFOS	
PAZOPANIB OR PLACEBO	800 MG PO DAILY, WEEKS 1-2						
PAZOPANIB MAINTEN- ANCE^G							1 WEEK AFTER COMPLETION OF CHEMO/RT (DURATION 52 WEEKS)

A Pazopanib versus placebo run-in 14 days

B Chemotherapy cycles every 21 days. Cycle 1 may not commence until a 6 day washout period of pazopanib has occurred.

C Cycles 3 and 4 will only be given if there is a response to chemotherapy identified on imaging after cycles 1 and 2.

D Pre-operative radiation administration, when given, will consist of external beam 50 Gy in 25 fractions of 2 Gy/fraction over 5 weeks. If the target volume encompasses sensitive structures such as bowel or lung, the dose can be reduced to 45 Gy in 25 fractions of 1.8 Gy without protocol violation.

E Surgery should be planned for 2-4 weeks after completion of pre-operative therapy. Any planned post surgical adjuvant chemotherapy should be initiated only after adequate wound healing has been achieved. Patients who require a delay of greater than 10 weeks from the initial surgery due to inadequate wound healing will be removed from further protocol therapy.

F Post-operative radiation administration, when given, will consist of external beam 50 Gy in 25 fractions of 2 Gy/fraction over 5 weeks, followed by 10 Gy boost (in 5 fractions) to a reduced, or boost, volume. For contaminated or close margins, the boost dose will be 10 - 16 Gy; for microscopically positive margins, 16 - 20 Gy, and for grossly positive margins, 20 – 26 Gy.

For patients who received pre-operative radiation, but have positive surgical margins, 16 – 20 Gy (2Gy x 8 - 10 fractions) will be given by external beam following any planned adjuvant chemotherapy.

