7.7.3 Chemotherapy Dose Modifications

A treatment cycle may not begin unless the patient's absolute neutrophil count (ANC) is $\geq 1500/\mu\text{L}$ and platelet count is $\geq 100,000/\mu\text{L}$ (without transfusion).

Patients who experience Grade 3 or 4 hematologic or non-hematologic toxicity that is attributable to chemotherapy and not to the underlying disease should have chemotherapy held until the toxicity resolves to \leq Grade 1. Dose modifications for doxorubicin and ifosfamide-related toxicity will be based on the Investigator's discretion.

Patients who are delayed greater than 3 weeks due to non-resolution of such toxicity will be taken off study.

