7.8 Criteria for Evaluability and Removal/Withdrawal from Treatment

Criteria for evaluability of the Trial

- Patients must have received a total of at least 80% of the intended dose of doxorubicin, ifosfamide, and pazopanib to be evaluable for the trial. If less than this amount is received, the patient may remain on the study, but will not be evaluated for primary endpoints.

Criteria for stopping therapy:

- Substantial non-compliance with the requirements of the study.
- Any adverse event which, in the Investigator's opinion, requires termination of the study medication.
- Disease progression, unless at the discretion of the Investigator (in collaboration with Novartis) continued treatment with study drug is appropriate.
- The patient would benefit from additional radiation therapy beyond that specified in the protocol.
- Request by the patient or a legal representative/relative to stop the treatment.
- The patient presents with a beta-HCG test consistent with pregnancy. Pregnancy will be reported along the same timelines as a serious adverse event.
- The patient uses illicit drugs or other substances that may, in the opinion of the Investigator, have a reasonable chance of contributing to toxicity or otherwise interfering with results.
- The development of a second malignancy that requires treatment, which would interfere with this study.
- The patient is lost to follow-up.
- Interruption in administration of pazopanib or chemotherapy for greater than 3-week delay.
- Development of an intercurrent illness or situation which would, in the judgment of the Investigator, affect assessments of clinical status and study endpoints to a significant degree.

Criteria for study withdrawal:

- Study closure.
- Patient decision to withdraw from both study therapy and follow-up.

The Investigator will make every reasonable effort to keep each patient in the study unless it is in the patient's best interest to discontinue participation. If a patient is removed from the study or declines further participation, all End of Treatment evaluations should be performed if the patient is willing and able to be assessed. A description of the reason(s) for withdrawal from the study will be recorded on the case report form (CRF). The Investigator should also ensure that all patients are followed up for survival and recurrence after the Final Visit.

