Relevant visit data should be entered on the CRF and any unused study medication will be accounted for and returned for all patients participating in the study, even for a brief period of time. Patients who discontinue following entry will have relevant information completed and recorded on the CRF. All patients who discontinue because of adverse events or clinically significant laboratory abnormalities should be followed up until they recover or stabilize, and the subsequent outcome will be recorded. If any patient should die during the trial or within 30 days of stopping study treatment, the Investigator will inform the IRB and the Novartis representative. The cause of death should be recorded in detail, within 24 hours, on a serious adverse event (SAE) form and reported to the IRB and Novartis.

Subjects who are withdrawn from the study prior to surgery will be replaced and randomized to treatment with pazopanib versus placebo according to the 2:1 design.

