11.0 ASSESSMENT OF EFFICACY

Evaluability: In order for a patient to be evaluable, 80% of the intended dose of all three drugs must be delivered in the first 2 cycles of chemotherapy.

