14.0 STATISTICAL CONSIDERATIONS

14.1 Analysis plan

The primary objective is to compare FDG SUV (SUV lean, SUL) measures for patients receiving pazopanib and placebo. The primary endpoint is the percent change in SUV between baseline and the end of the 14-day Run-in period of pazopanib or placebo. The comparison will likely be conducted using a two-sided Wilcoxon rank sum test, often used as a nonparametric alternative to the two-sample t-test for studies with a small sample size. Additional endpoints will include SUV percentage change between baseline and the end of preoperative therapy, absolute post-treatment SUV (at 14 days and following preoperative chemotherapy), and absolute difference in SUV.

The analysis sample for the primary pharmacodynamic analysis is expected to exclude patients who have incomplete data due to missed PET scans or due to study withdrawal for toxicity. However, reasons for missing data will be examined, and multiple imputation will be considered if patients with incomplete data would be considered as part of the target population for future development of pazopanib in sarcoma. However, insofar as sarcoma is heterogeneous, the sample size is small, and covariates are limited – multiple imputation may not be applicable.

These pharmacodynamic response measures will be compared to tumor response by RECIST criteria, using graphical displays. Continuous measures of pharmacodynamic response (percentage change in SUL; response assessed using MRI) will also be compared to the trough plasma pazopanib, using graphical displays and correlation coefficients to investigate dose-response relationships related to patients' differing metabolism of pazopanib.

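### The replacement rule in section 7.8 turns on withdrawal before surgery, not on having the week-2 PET pair, so patients excluded from the primary analysis who stay on study are not replaced

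*Combined protocol and SAP*

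**What the plan says.** Replacement is governed by one sentence at the end of section 7.8: "Subjects who are withdrawn from the study prior to surgery will be replaced and randomized to treatment with pazopanib versus placebo", again at 2:1. The trigger is study withdrawal at any time before surgery. Section 7.0 sets the timing of surgery: "Surgery should be planned for 2-4 weeks after completion of pre-operative therapy".

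Section 14.1 fixes the endpoint much earlier: "The primary endpoint is the percent change in SUV between baseline and the end of the 14-day Run-in period of pazopanib or placebo". The analysis sample is "expected to exclude patients who have incomplete data due to missed PET scans or due to study withdrawal for toxicity".

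Two further passages decide who counts. Section 7.8 requires at least 80% of the intended doxorubicin, ifosfamide and pazopanib; for a patient below that, "the patient may remain on the study, but will not be evaluated for primary endpoints". Section 11.0 puts the same threshold differently: "80% of the intended dose of all three drugs must be delivered in the first 2 cycles of chemotherapy".

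Section 14.2 bases about 90% power on 21 patients randomized 2:1, and the enrolment table in section 14.3 also totals 21. No passage links replacement to having the PET pair, or says whether a replaced patient's scans stay in the primary analysis.

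**The concern.** A replacement rule should make good the losses that reduce the primary comparison and leave alone those that do not. This one is keyed to a later event, and it misses in both directions.

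First, a patient with both scans who withdraws during pre-operative chemotherapy or radiation is replaced although the week-2 change is already known. The plan does not say whether the replacement adds to that patient's data or takes their place.

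Second, a patient who misses the post-Run-in PET but continues to surgery is excluded by section 14.1 and, not being withdrawn, is not replaced. The same holds for a patient below 80% dose who remains on study.

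The 80% rule raises a related problem. Most of the dosing it counts is chemotherapy given after the week-2 PET. Applied to the primary endpoint, it selects the randomized comparison on events that follow the measurement. Those events may differ by arm: the safety of pazopanib followed by chemotherapy is itself a secondary objective (section 3.2).

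**Working it through.** **Timing.** From the section 7.0 table, cycles 1 and 2 end at week 8. Surgery 2–4 weeks later falls at weeks 8 + 2 = 10 to 8 + 4 = 12. With cycles 3 and 4 and pre-operative radiation ending at week 21, it falls at weeks 21 + 2 = 23 to 21 + 4 = 25. The Run-in ends at week 2, so the replacement trigger stays open for about 10 − 2 = 8 to 25 − 2 = 23 weeks afterwards.

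**Who is replaced and who is analysed.**

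| Patient | Replaced under 7.8? | In the week-2 analysis? |
|---|---|---|
| Withdraws in the Run-in before the second PET | Yes | No (14.1) |
| Both PETs, withdraws before surgery | Yes | Complete under 14.1; may fail the 80% rule |
| Misses the post-Run-in PET, goes on to surgery | No | No (14.1) |
| Below 80% dose, stays on study | No | No (7.8, 11.0) |

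Only the first row behaves as a replacement rule for this endpoint should. On the second row, a patient with both scans who receives one of the first two chemotherapy cycles in full has had 1/2 = 50% of the intended dose. That is below 80%, so section 11.0 makes the patient non-evaluable despite a complete week-2 change.

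**Power.** Inputs from section 14.2: difference 30 points, SD 20, n = 21 at 2:1, hence 14:7. Section 14.1 gives a two-sided test. No alpha is stated; 0.05 is assumed. The normal formula is

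power = Φ(30 / (20·√(1/a + 1/b)) − 1.96).

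- 14:7: 20·√(1/14 + 1/7) = 9.258; 30/9.258 = 3.240; Φ(1.280) = 89.98%. This reproduces the stated figure.
- 13:6: 20·√(1/13 + 1/6) = 9.871; 30/9.871 = 3.039; Φ(1.079) = 86.0%.
- 12:6: 20·√(1/12 + 1/6) = 10; 30/10 = 3; Φ(1.04) = 85.1%.

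The second set of figures below is for the Wilcoxon test that section 14.1 says will likely be used (exact test, normal data, 40,000 simulated trials per split).

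| Analysed (pazopanib:placebo) | Normal formula | Wilcoxon |
|---|---|---|
| 14:7 | 90.0% | 83.6% |
| 13:7 | 89.2% | 82.4% |
| 12:7 | 88.4% | 80.8% |
| 13:6 | 86.0% | 77.6% |
| 12:6 | 85.1% | 74.7% |
| 10:5 | 78.2% | 64.1% |

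The gap between 90.0% and 83.6% at 14:7 comes from the choice of test and not from replacement; the cost of losses is read down each column. A placebo loss costs more than a pazopanib loss (13:6 against 12:7).

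The loss counts are assumptions, as the documents give no attrition rate. In the other direction, if three patients are replaced and their own scans are kept, the set could be 16:8, with 93.4% by the normal formula and 24 enrolled in place of 21.

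**The case against.** The strongest defence is that the week-2 change is not the only endpoint called primary. Sections 3.1, 4.2.1 and 11.1 also list SUV after two chemotherapy cycles, and sections 3.1 and 4.2.1 list RECIST response. Necrosis at surgery is secondary, with a 90% interval planned in section 14.1. In a 21-patient pilot, replacing until surgery is a reasonable way to protect these. This stands as a reason not to abolish late replacement. It does not justify leaving patients without a week-2 endpoint unreplaced: n = 21 is justified only by percent change in SUV, and section 14.1 names the week-2 change as the primary endpoint.

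Three stronger readings are tempting and are not supported.

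- A reader might infer that no patient lacking the endpoint is replaced. Withdrawal during the Run-in precedes surgery and does trigger replacement.
- A reader might infer that a replaced patient's scans are discarded, which would bias the comparison. No passage says so. Section 14.1 excludes incomplete data, a patient with both scans is complete for week 2, and section 7.8 has relevant data recorded for patients who discontinue. The text that can remove such a patient is the 80% rule.
- A reader might infer that a chemotherapy delay certainly leads to replacement, since section 7.7.3 says: "Patients who are delayed greater than 3 weeks due to non-resolution of such toxicity will be taken off study". But section 7.8 lists the same delay under stopping therapy. Its separate list for study withdrawal has only study closure and "Patient decision to withdraw from both study therapy and follow-up". The two sections must be reconciled. On the strict reading, a patient who stops drug for Run-in toxicity, misses the PET and stays in follow-up is not replaced either.

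Section 14.1 does say that multiple imputation will be considered, but it doubts that the method will be applicable in a small, heterogeneous sample with few covariates. It cannot be relied on to restore the lost information.

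**Conclusion.** The point holds in a limited form. The replacement trigger is not tied to the week-2 endpoint. It may replace patients who have that endpoint, is silent on keeping their data, and leaves unreplaced those who are excluded but stay on study. With planned enrolment equal to the power N, two unreplaced losses (13:6) take the stated 90% to 86.0% and three (12:6) to 85.1%. Under the Wilcoxon test the fall is from 83.6% to 77.6% and 74.7%. These figures rest on the section 14.2 effect and SD, an assumed two-sided 0.05 and assumed loss counts. One pazopanib loss costs little (89.2%).

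The 80% rule matters separately, because it conditions the randomized comparison on dosing after the outcome is known. The size and direction of any bias cannot be calculated from the documents. The change is cheap and protects the only comparison the sample size was built for, so it should be made.

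**What to change.** 1. In section 7.8, extend replacement to any randomized patient without a valid baseline plus post-Run-in PET pair, whether or not the patient continues to surgery.
2. In sections 7.8, 11.0 and 14.1, state that every randomized patient with a valid pair is analysed for the week-2 percent change in the assigned arm, whatever the later chemotherapy dose or withdrawal; that a replacement never displaces existing data; and that the 80% chemotherapy-dose rule does not apply to this endpoint. All three sections need the wording, since otherwise the 80% text would contradict the new rule.
3. Leave to the sponsor whether patients withdrawn after week 2 are still replaced. Keeping this supports the post-2-cycle SUV and necrosis endpoints; dropping it saves enrolment. The choice should be written down, along with what counts as withdrawn for this purpose.

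The cost is a short amendment to three sections. The downside is a few extra enrolments if patients without a PET pair are replaced in addition to late withdrawals.

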8.0 GUIDELINES FOR ADVERSE EVENT REPORTING

8.1 Adverse Event Reporting/ Institutional Policy

In accordance with institutional policy, all adverse events which in the opinion of the Principal Investigator are unexpected **and** related or possibly related to the research **and** serious or suggest that the research places research participants or others at greater risk of physical or psychological harm than was previously known or recognized be reported to the IRB within 10 calendar days of learning of the problem.

Definitions:

Adverse Event: - Any untoward medical occurrence in a patient or clinical investigation subject administered a pharmaceutical product, medical treatment or procedure and which does not necessarily have to have a causal relationship with this treatment. An adverse event can therefore be any unfavorable and unintended sign (including an abnormal laboratory finding, for example), symptom, or disease temporally associated with the use of a medicinal product, medical treatment or procedure whether or not considered related to the medicinal product.

Life-threatening Adverse Event: – Any adverse event that places the patient or subject, in view of the Investigator, at immediate risk of death from the reaction.

Unexpected Adverse Event: – An adverse event is “unexpected” when its nature (specificity), severity, or frequency are not consistent with (a) the known or foreseeable risk of adverse events associated with the research procedures described in the Protocol-related documents, such as the IRB-approved research protocol, informed consent document and other relevant sources of information such as product labeling and package inserts; and are also not consistent with (b) the characteristics of the subject population being studied including the expected natural progression of any underlying disease, disorder or condition any predisposing risk factor profile for the adverse event.

Serious Adverse Event (SAE): – Any adverse event occurring that results in any of the following outcomes:

- death;
- a life-threatening adverse event (real risk of dying);
- inpatient hospitalization or prolongation of existing hospitalization (for reasons other than planned chemotherapy or post-surgical care)
- a persistent or significant disability/incapacity;
- a congenital anomaly;
- requires intervention to prevent permanent impairment of damage.

Attribution: - The following are definitions for determining whether an adverse event is related to a medical product, treatment or procedure:

An adverse event is “**related or possibly related to the research procedures**” if in the opinion of the Principal Investigator, it was more likely than not caused by the research procedures.

Adverse events that are **solely** caused by an underlying disease, disorder or condition of the subject or by other circumstances unrelated to either the research or any underlying disease, disorder or condition of the subject are **not “related or possibly related.”**

If there is any question whether or not an adverse event is related or possibly related, the adverse event should be reported.

The Cancer Consortium Expedited Reporting Form should be completed for all adverse events that meet the expedited reporting requirements. The AE form should be faxed to the IRO at [contact]. All available information should be submitted.

It is the responsibility of the Principal Investigator and/or a designated staff member to notify Novartis, NIH, and the FDA of adverse events that meet expedited reporting (such as Serious Adverse Events) as required in the protocol.

Also considered serious for the purposes of this study:

- ALT $>3.0 \times$ ULN with concomitant elevation in bilirubin (defined as total bilirubin $<2.0 \times$ ULN or direct bilirubin 35%) or with hypersensitivity symptoms (e.g., fever, rash) – bilirubin fractionation should be performed in testing available.
- ALT $>8.0 \times$ ULN without bilirubin elevation (defined as total bilirubin $<2.0 \times$ ULN or direct bilirubin 35%) and without hypersensitivity symptoms (e.g., fever, rash) – bilirubin

fractionation should be performed if testing available.

Serious Adverse Events

For Open Label Portion of Study:

All SAEs arising during the study in subjects exposed to pazopanib will be reported to Novartis using copies of the original Case Report Form pages and within 24 hours of first becoming aware of the event, regardless of causality assessments.

For Blinded Portion of Study:

Study conduct procedures will be ensured and in place to allow for the expedited reporting of relevant SAEs to the appropriate regulatory authorities, IEC(s) or IRB(s) as required, during the course of the study.

SAEs will be sent to Novartis as they arise in subjects exposed to pazobanib using copies of the original Case Report Form pages and within 24 hours of first becoming aware of the event, regardless of causality assessments.

Pregnancy Reports

Reports of pregnancy information on any female subjects who becomes pregnant while participating in the study and following exposure to the study product will be sent to Novartis using copies of the original Case Report Form pages and within two weeks of the pregnancy (including premature termination of the pregnancy).

Information on the status of the mother and child will be reported to the coordinating center. Generally, follow-up will be requested by Novartis no longer than 8 weeks following the estimated delivery date.

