7.7.2 Dose Interruptions/Modifications for Hepatotoxicity

AST, ALT and/or Bilirubin	
Isolated AST/ALT elevations between 3X ULN and 8X ULN	Reduce pazopanib dose to 200 mg QD, and monitor weekly until AST/ALT returns to ≤ 2.5 or baseline
AST/ALT >8 X ULN	Hold pazopanib until AST/ALT returns to ≤ 2.5 X ULN or baseline. If the potential benefit of reinitiating pazopanib treatment is considered to outweigh the risk for hepatotoxicity, then consider reintroducing pazopanib at a reduced dose of 400 mg once daily and measure serum liver tests weekly for 8 weeks only after discussion with the PI . If AST/ALT elevations >3 X ULN recur, then pazopanib should be permanently discontinued.
AST/ALT >3 X ULN and concurrent bilirubin elevations >2 X ULN	Permanently discontinue pazopanib.
Mild indirect hyperbilirubinemia, known or suspected Gilbert's syndrome, and elevation in AST/ALT >3 X ULN	Continue pazopanib, but monitor weekly until AST/ALT returns from >3 X ULN to grade 1 (NCI CTCAE) or baseline.

Severe hepatic impairment, defined as bilirubin >3 X ULN, regardless of any level ALT	Permanently discontinue pazopanib.
---	------------------------------------

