8.2 Study-Specific Adverse Event Capture

8.2.1 Duration and Grade of Adverse Event Capture

All grade 3 and 4 adverse events occurring after the subject has taken the first dose of study drug until the end of study will be recorded in the subject's case record form.

Documentation must be supported by an entry in the subject's file. A laboratory test abnormality considered clinically relevant, e.g., causing the subject to withdraw from the study, requiring treatment or causing apparent clinical manifestations, or judged relevant by the Investigator, should be reported as an adverse event. Each grade 3 or 4 event should be described in detail along with start and stop dates, severity, relationship to investigational product, action taken and outcome.

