Descriptive displays of preliminary clinical endpoints (pathologic response, progression-free survival, overall survival) will compare response for the pazopanib and placebo groups, and will investigate the relationship between early pharmacodynamic response (by PET) and clinical endpoints. Response of high-risk soft tissue sarcoma to neoadjuvant chemoradiation therapy was estimated as 52% (38% no residual tumor, 14% ≥ 95 pathologic necrosis) in a series of 496 patients.[9] A smaller series found only 13/46 (28%) with $< 10\%$ viable tumor in surgical specimens following a variety of neoadjuvant regimens.[51] To direct planning of future studies, we will measure the rate of complete pathological response defined as greater than 95% necrosis in the surgical excision specimen. A 90% Wilson (score) binomial confidence interval will be computed for the rate of complete pathological response.

There are no stopping rules planned for toxicity, but safety will be monitored continuously. All subjects who are registered and receive at least one dose of study drug will be included in the safety analysis.

All reported adverse events will be coded using the Cancer Therapy Evaluation Program (CTEP) Common Toxicity Criteria version 4.0. The number and percent of subjects reporting adverse events (all, severe or worse, serious and related) will be quantified. Listings will be provided for all on-study deaths and adverse events that lead to withdrawal from study. Narratives of all serious adverse events and deaths on-study will be provided.

Correlative study assays will be analyzed using descriptive statistics, generally comparing pazopanib and placebo groups. Correlation will also be evaluated between pazopanib trough concentrations and drug exposure over the dosing interval (area-under-the-concentration-curve, AUC) in subjects consenting to the full intensive pharmacokinetic visits.

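### Section 8.1 uses the same inequality, total bilirubin below 2.0 × ULN, to define both the presence and the absence of bilirubin elevation in the hepatic SAE criteria, and its first bullet runs opposite to Section 7.7.2

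*Combined protocol and SAP*

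**What the plan says.** After the general SAE outcomes, Section 8.1 lists two hepatic laboratory patterns that also count as serious in this study.

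- **First bullet:** ALT >3.0 × ULN "with concomitant elevation in bilirubin (defined as total bilirubin $<2.0" × ULN, or hypersensitivity symptoms.
- **Second bullet:** ALT >8.0 × ULN "without bilirubin elevation (defined as total bilirubin $<2.0" × ULN, and no hypersensitivity symptoms.

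Both parentheses also offer an alternative limb, direct bilirubin at 35%, with no comparison sign in the text available for review.

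The hepatotoxicity table in Section 7.7.2 treats bilirubin elevation as a value above a limit. Its combined row pairs AST/ALT >3 × ULN with concurrent bilirubin "elevations >2 X ULN" and calls for permanent discontinuation. A separate row, "Isolated AST/ALT elevations between 3X ULN and 8X ULN", carries dose modification and weekly monitoring.

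For subjects exposed to pazopanib, Section 8.1 sends SAEs to the drug supplier "within 24 hours of first becoming aware of the event, regardless of causality assessments". In the analysis, Section 14.1 states: "The number and percent of subjects reporting adverse events (all, severe or worse, serious and related) will be quantified". It also requires a narrative for every SAE.

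**The concern.** A single condition cannot mean both that bilirubin is elevated and that it is not. In the second bullet, below 2.0 × ULN is a sensible description of no elevation and agrees in direction with Section 7.7.2. The fault therefore lies in the first bullet, whose words say elevation and whose inequality says the reverse.

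These bullets decide which laboratory-only liver events are serious. Read literally, a patient with ALT >3 × and bilirubin ≥2 × ULN does not qualify through total bilirubin, although Section 7.7.2 discontinues the drug once bilirubin exceeds 2 × ULN. An isolated 3–8 × ALT rise with bilirubin below 2 × ULN does qualify.

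Other provisions do not clearly close the gap. Stopping the drug is not itself one of the general SAE outcomes. The 10-day IRB route in Section 8.1 applies only to unexpected events, and Section 10.1 lists raised ALT and raised bilirubin as expected.

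Liver toxicity is also a known risk of this drug. Section 2.4 names raised ALT and AST among the most frequent grade 3 events and among the commonest reasons for permanent discontinuation. Section 14.1 plans no toxicity stopping rule, so oversight depends on events being classified consistently. Section 9.1 names two institutions whose records are monitored, and they could apply the text differently.

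**Working it through.** The plan states no figure to reproduce; the check is on the logic of the definitions.

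**Rules compared**

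- *Literal rule (8.1 as printed).* Bullet 1: ALT >3 and (bilirubin <2, or direct limb, or hypersensitivity). Bullet 2: ALT >8 and (bilirubin <2, or direct limb) and no hypersensitivity.
- *Comparison rule.* The same two bullets, with elevation meaning bilirubin ≥2 (or the direct limb, where available). The value ≥2 is simply the complement of the printed <2.0. It shows which cases change and is not a proposed threshold. Section 7.7.2 uses >2, so the two differ only at exactly 2 × ULN.

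All values are multiples of ULN.

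**Step 1. No hypersensitivity, no fractionation result, no general SAE outcome**

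| ALT | Total bilirubin | Literal 8.1 | Comparison | Agree? |
|---|---|---|---|---|
| 3–8 | <2 | serious (bullet 1) | not serious | no (added) |
| 3–8 | ≥2 | not serious | serious | no (missed) |
| >8 | <2 | serious (both bullets) | serious | yes |
| >8 | ≥2 | not serious | serious | no (missed) |

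Discordant: 1 added + 2 missed = 3 of 4.

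For example, ALT 4 with bilirubin 0.8 is serious as a case with bilirubin elevation, while ALT 4 with bilirubin 2.5 is not.

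**Step 2. Redundancy.** As printed, bullet 2 is {ALT >8, bilirubin <2}. It lies wholly inside bullet 1, {ALT >3, bilirubin <2}, so it adds no case.

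**Step 3. Overlap with the combined row of 7.7.2.** On a grid in steps of 0.1, with ALT up to 25 and bilirubin up to 10, ALT >3 gives 220 values and bilirubin >2 gives 80, so 220 × 80 = 17,600 points. None meets either 8.1 bullet through total bilirubin as printed; all 17,600 do under the comparison rule. This sets aside the separate 7.7.2 row for mild indirect hyperbilirubinemia or Gilbert's syndrome.

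**Step 4. Direct-bilirubin limb available.** Splitting each cell by direct bilirubin gives 2 × 2 × 2 = 8 cells. The sign is an assumption.

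- *Read as above 35%.* Every cell with direct bilirubin above 35% is serious under both rules. The other four cells repeat the table in Step 1, so 3 of 8 differ.
- *Read as below 35% in both rules.* Every cell below 35% is serious under both rules. The remaining four repeat the table, so again 3 of 8 differ.

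The count does not depend on the sign; which patients are affected does.

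**Step 5. Hypersensitivity present.** Bullet 1 admits every ALT >3 case under both rules, so 0 of 4 differ.

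**The case against.** The strongest objection is that this may be a one-character reading error. The text was machine-read from PDF, and the sign before 35% is absent in the same parenthesis, so symbols may have been lost there. That is a reason to check the printed page first. It does not dispose of the point: the ALT comparison signs in these bullets were read, the same inequality appears in both, and no other section corrects it. Duplicated wording looks at least as likely, though that is inference. The missing sign before 35% is not counted as an error here.

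A second objection is that a sensible reader would follow the words rather than the sign, and that Section 7.7.2 is a dose table using AST/ALT, which need not match a seriousness definition using ALT alone. Both are fair. The two sections need not rank events identically, and only the first bullet opposes 7.7.2. But the contradiction within 8.1 stands without 7.7.2, and a reporting rule should not rely on readers overriding its printed limit.

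Third, other safeguards exist. The general outcomes still apply, including an event that "requires intervention to prevent permanent impairment of damage". Hypersensitivity symptoms bring in any ALT >3 × case. Section 8.2.1 records "All grade 3 and 4 adverse events occurring after the subject has taken the first dose of study drug" and also clinically relevant laboratory abnormalities. Section 7.7.2 still identifies the affected patients, and Section 9.2 provides bi-monthly review. This limits the harm: the signal is not lost. What remains exposed is expedited routing and SAE classification for laboratory-only liver events.

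**Conclusion.** The concern holds: the first hepatic bullet of Section 8.1 is wrong as written and should be fixed. It contradicts its own wording and the second bullet, runs opposite to Section 7.7.2, and makes the second bullet redundant. The 3-of-4 discordance assumes that neither hypersensitivity symptoms, nor a fractionation result, nor a general SAE outcome decides the case. It becomes 3 of 8 with fractionation and 0 of 4 with hypersensitivity.

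These fractions count unweighted logical cells and must not be read as an error rate in patients. The documents give no basis for estimating how many subjects would fall in each cell. The conclusion also assumes that the printed page carries the sign as read here. The consequence is confined to safety reporting and SAE counts; the primary PET comparison and the sample size are untouched.

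**What to change.** Check the printed source of both bullets. If the sign stands, correct the direction of the total-bilirubin inequality in the first bullet so that it describes an elevation. In each bullet, confirm or state the direction of the direct-bilirubin 35% limb. The sponsor should reconcile Section 8.1 with Section 7.7.2 and state the threshold values; none is proposed here. The cost is a source check and a one-line text correction, with no added data, patients or analyses.
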